### 2.3.2 KNOWN POTENTIAL BENEFITS

The potential benefits to patients include: a reduction in symptomatic UTIs, a reduction in use of oral antibiotics used to treat UTI, and an improved quality of life. Successful treatment is likely to enable persons with SCI to live more active, independent and productive lives, contributing to the fabric of society. A 2009 study found that treatments leading to favorable urodynamic results correlated with better quality of life in those with SCI. Neurogenic bladder in general and UTIs in specific lead to increased mortality and morbidity in the SCI population, along with greater incidence of hospitalizations.

Successful treatment can decrease morbidity, mortality and hospitalizations related to UTIs. With fewer medical complications associated with neurogenic bladder (i.e. incontinence and leakage) and bowel (i.e. constipation and incontinence), patients are more likely to live healthy, happy and fulfilling lives.

The potential for benefit extends to caregivers who might experience reduced stress or concern for UTIs, and to clinic staff who might experience fewer telephone encounters from patients related to UTI concerns.

### 2.3.3 ASSESSMENT OF POTENTIAL RISKS AND BENEFITS

The risk-benefit profile of using daily bladder instillations of gentamicin is favorable. In patients for whom frequent UTIs are a problem, intravesical treatment with gentamicin offers a minimally

burdensome strategy with minor increase over minimal risk.

### 3 OBJECTIVES AND ENDPOINTS

OBJECTIVES	ENDPOINTS	JUSTIFICATION FOR ENDPOINTS
Primary		
The use of intravesical gentamicin reduces the incidence of UTIs during treatment	A reduction in the count of UTIs during the six months of treatment	Allows for verification of reduced UTIs during the intervention. UTIs are associated with major medical, psychological, social and economic consequences
Secondary		
Gentamicin treatment will decrease self-reported bladder complications	A reduction in scores of the Neurogenic Bladder Symptom Severity at six months of gentamicin use.	Allows for validated self-assessment of bladder symptoms in patients with SCI following the intervention.
Gentamicin treatment will decrease self-reported bowel complications	A reduction in scores of the Neurogenic Bowel Dysfunction at six months	Allows for a validated self-assessment of bowel dysfunction severity in patients with SCI following the interventions
Tertiary/Exploratory (other pre-specified analyses)		
The use of intravesical gentamicin will enhance overall quality of life	An increase in SF-Qualiveen scores at six months of gentamicin use	UTIs, associated bladder and bowel complications contribute to reduced QOL in patients with SCI manifesting in negative affect and psychological functioning
The use of intravesical gentamicin will enhance quality of life by decreasing bladder management difficulties	An improvement in SCI-QOL: Bladder Management scores at six months.	
The use of intravesical gentamicin will enhance quality of life by decreasing bladder complications	An improvement in SCI-QOL: Bladder Complications scores at six months.	
The use of intravesical gentamicin will enhance quality of life by decreasing bowel management difficulties	An improvement in SCI-QOL: Bowel Management Difficulties scores at six months.	
The use of intravesical gentamicin will increase overall community participation	An improvement in Community Participation Indicators Scale scores at six months.	Repeated UTIs, associated bladder and bowel complications negatively impact patients' interactions with their social environments
The use of intravesical gentamicin will increase subject's satisfaction with roles and activities scale	An improvement in SCI-QOL: Satisfaction with roles and activities scale scores at six months.	

## 4 STUDY DESIGN

### 4.1 OVERALL DESIGN

#### KEY DESIGN DETAILS

- Hypothesis - The use of intravesical gentamicin will reduce the incidence of UTIs, bladder complications, bowel complications, and will enhance subject's quality of life.
- Pre-post study design, comparing participants number of UTIs during the six-month treatment period to the number they incurred during the six months prior to treatment.
- Participants will begin with active treatment, using gentamicin + saline solution, after they have completed the baseline interview and required urinalysis and bloodwork.
- Phase 2/3
- Single-site - Michigan Medicine in Ann Arbor, MI.
- Dosing – Instillations of treatment solution will occur nightly after the subject's last evening catheterization.
- Interim analysis – The study design and intended sample size preclude meaningful interim analyses.

#### HYPOTHESES

The proposed study is a pre- post CT in which participants receive the study drug for six calendar months, and analysis compares their frequency of UTIs during this period to the frequency in the prior six months:

1. The incidence of UTIs will be lower during the treatment period than it had been during the previous six calendar months. Occurrence of UTIs throughout this study will be defined as having symptoms of a UTI, followed by a positive urine culture and prescribed treatment.
2. The number of bladder and bowel complications will be likewise decreased during the treatment period compared to what was reported during the baseline interview.
3. Reported health-related quality of life will be higher during the treatment period compared to the how it was reported during the baseline interview.
4. Satisfaction with social roles and activities and community participation will be higher during the treatment period than how it had been reported during the baseline interview.

 Throughout this document, six months refers to 180 calendar days.

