*Confidentiality breach* – The risk of research data or PHI being accessed without study or clinical care need is very low given the standard safeguards used by Michigan Medicine as an institution and by those on the study team. Access to study-related files is granted on the basis of need by the project manager. Electronic files, including electronic consents, are protected by the Michigan Medicine information technology infrastructure, which includes digital encryption, and paper files are stored in a secure environment including locked file cabinets and restricted access offices.

*Toxicity* – The likelihood that a participant in this study would experience toxicity is quite low, as toxicity as a side effect is more associated with high doses of prolonged systemic therapy and/or in patients with impaired renal function. While high doses of gentamicin and similar compounds can be associated with nephro- and ototoxicity, these risks are minimized in this study due to the exclusion of patients with renal impairment and because the systemic absorption via the bladder has been found to be negligible. Using rats, canines and humans, Wan (1994) instilled gentamicin and evaluated serum

levels 30-minutes post-instillation. Only the rat model showed measurable, yet low, non-toxic levels of serum gentamicin; neither canine nor human tests showed any detectable concentration. In studies with limited follow-up data, there were no clinically relevant side effects. While unlikely based on these factors, gentamicin toxicity may manifest in the form of new onset and prolonged numbness, skin tingling, dizziness and vertigo. Other side effects include prolonged muscle twitching, tinnitus, roaring in the ears or hearing loss. Subjects will be instructed to remain well hydrated during study treatment, and to discontinue treatment if they experience any of these symptoms and to contact the study coordinator.

*Overdosage* – Overdosage may increase the risk of toxicity described above. The risk of this is minimal as long as subjects take study treatment as directed. As stated above, the localized dosing is unlikely to cause any increase in serum gentamicin levels and, additionally, the dose of gentamicin in each syringe is far below the threshold at which has been reported to cause adverse reactions.

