## 4.3 JUSTIFICATION FOR DOSE

### GENTAMICIN + SALINE

The research pharmacy will send participants premixed bags of 60mg of gentamicin in 50ml of normal saline. Participants will draw 25cc with their syringe, switch tips, instill this into the bladder after emptying of urine at their last evening catheterization, and discard the remaining 25cc of premixed solution. This is equivalent to the 30mg which had been used in the initial study protocol. The solution will remain in the bladder until the next catheterization. This is a standard dose that is easily tolerated by patients, and one that does not lead to leakage. It is based on the clinical expertise of Co-I, [name], and is appropriate for bladders sizes in patients with long-term use of indwelling catheterization.

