#### **6.1.2 DOSING AND ADMINISTRATION**

The study treatment will either be self-administered or administered by a caregiver. During treatment participants will be instructed to follow their normal catheter routine for bladder emptying at night, before bed. Once the bladder is empty, participants will attach the syringe containing the study product to the end of the catheter and slowly push the solution into the bladder. Once the full dose is instilled into the bladder, the participant will remove the catheter and syringe, leaving the study product in the bladder until the following morning. Participants will be asked to document the date and time of instillation and the date and time of bladder emptying the next morning in their daily dosing log, along with any other comments related to the process or related observed complications. In summary the process involves:

1. Emptying the bladder as usual at night, before bed
2. Attaching the catheter tip to the syringe
3. Flushing the bladder with the solution
4. Discarding the catheter tip and disposing of used syringe
5. Leaving the solution in place until next routine bladder emptying
6. Emptying the bladder with catheter as usual at next routine bladder emptying the next morning

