#### **Treatment condition: gentamicin + saline**

- Instillation dose of 25mL solution every day; gentamicin dose = 30mg.
- Instillation to occur at night after the last bladder emptying of the day before bed.
- Self or caregiver administered via catheter.
- To remain in the bladder until next catheterization.

To ensure proper administration, participants and their caregivers will receive training on how to conduct the daily instillations. This training and printed information that includes contact information

for the study team will be provided to participants. A blank copy of the daily dosing log will be included as well. The process will also be explained to them when they enter the study.

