## 8 STUDY ASSESSMENTS AND PROCEDURES

### 8.1 EFFICACY ASSESSMENTS

*Section 8.1 refers to lab visits and study interviews. It will be standard practice to conduct as many procedures remotely as possible to better protect subject/caregiver(s) and UM staff against the risk of COVID-19. However, in cases where a procedure cannot be conducted remotely (e.g., required in-person lab visits for blood draws), the study coordinator will educate study participants/caregivers on all of Michigan Medicine's safety guidelines for entering and being in UM buildings (e.g., COVID screenings, PPE, social distancing, etc.).*

**Demographics, Clinical History and Current Medications** will be abstracted from the electronic medical record and confirmed with participant and caregiver during study interviews. Co-morbidities, bladder and bowel symptoms, and current medications will be recorded. Elements specific to SCI include age at injury and level and completeness of neurological impairment. Changes in health status and medication use will be updated during each interview.

**Urine analysis** – Prior to any MLabs visit, the study coordinator will remind the participant of Michigan Medicine's policies regarding COVID-19 as they relate to the participant and any person whom they might need to accompany them. Participants will provide urine samples according to MLabs (Michigan Medicine Pathology Handbook) specifications. A clean urine analysis is required for enrollment. Minimum volume required is 0.5ml collected in a non-sterile plastic urine cup. Dipstick analysis may be performed in the clinic at the time of the baseline visit; results are usually available within 10-15 minutes. Tests that come back positive will be sent to the lab for a urine culture. Specimens can be stored at room temperature if received in lab within 2 hours of collection; otherwise the sample should be refrigerated for up to 24hr. Results are usually back within 4 days for a culture.

**Self-reported quality of life measures** will be collected twice: at baseline and after the treatment period (approximately six months). Several disease-specific and overall quality of life measures will be used, including several scales from the SCI-QOL Measurement System. The SCI-QOL system builds on the PROMIS and Neuro-QOL initiatives were developed to address a dearth of valid patient-reported outcome measures for patients with spinal cord injury.

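### The primary UTI count requires a positive culture, but only treatment-period urine can contain instilled gentamicin, so residual drug may bias the pre-post rate ratio toward benefit by an unknown amount

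*Protocol*

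**What the plan says.** The design is pre-post without a concurrent arm, "comparing participants number of UTIs during the six-month treatment period to the number they incurred during the six months" before it (Protocol, Section 4.1, Key Design Details). The Hypotheses part of that section defines the event: "Occurrence of UTIs throughout this study will be defined as having symptoms of a UTI, followed by a positive urine culture and prescribed treatment". All three elements are needed.

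Exposure differs between the two periods:

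- **Treatment period.** "Instillations of treatment solution will occur nightly after the subject's last evening catheterization" (Section 4.1). The amount is given in Section 6.1.2: "Instillation dose of 25mL solution every day; gentamicin dose = 30mg". The participant removes the catheter, "leaving the study product in the bladder until the following morning" (Section 6.1.2); Section 4.3 agrees: "The solution will remain in the bladder until the next catheterization". Section 2.3.1 argues that toxicity is unlikely in part "because the systemic absorption via the bladder has been found to be negligible", which implies that the drug stays mainly in the urine.
- **Comparison period.** Section 5.2 excludes people who used systemic or intravesical antibiotic prophylaxis in the previous six months.

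Instillations pause only while an outside antibiotic is being taken (Sections 6.5 and 6.5.1). On specimens, Section 8.1 says "Participants will provide urine samples according to MLabs (Michigan Medicine Pathology Handbook) specifications". Nothing in the protocol or SAP links the timing of a diagnostic specimen to the last instillation, or says how a symptomatic, treated, culture-negative episode is handled.

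Section 10.1.9.1 names the medical record as the source for UTI counts. Neither Section 9.4 nor the SAP contains a UTI count that does not depend on culture. The only sensitivity analysis mentioned (Section 9.4.3) is optional and concerns missing data.

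**The concern.** An antibacterial in the specimen can affect the test that decides whether an event is counted, and here it can be present in one period only. That is a possible difference in outcome ascertainment between the two halves of the single primary comparison. Where it operates, it removes events from the treatment period and lowers the rate ratio.

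Three features of the plan leave it unexamined. There is no concurrent arm. The primary population in Section 9.3 requires use on at least half of the days, which concentrates the comparison on exposed participants. The SAP's post-treatment periods do not separate the explanations, because a rise in counted UTIs off drug would fit both lost prevention and lost masking.

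**Working it through.** **The plan's own figure.** Section 9.2 gives 15 completers for at least 80% power to detect a 50% reduction, using a paired t-test on log rates. The standard deviation of the within-person log difference is not stated, so the 15 can only be solved backwards. With a difference of ln 2 = 0.693, it implies a standard deviation of about 0.89 (two-sided) or 1.03 (one-sided). It can be neither confirmed nor faulted, and the point below does not depend on it. What matters is the design effect, a rate ratio of 0.50.

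**Step 1: drug in the specimen.** From the documents: 30 mg in 25 mL, so 30,000 µg / 25 mL = 1,200 µg/mL as instilled. Assumed, because the documents do not give them: 300 to 600 mL of overnight urine, no absorption, 10 mL residual after emptying, 400 mL refill.

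- First-morning specimen: 30,000 / (25 + 300) = 92 µg/mL; 30,000 / (25 + 600) = 48 µg/mL.
- After one emptying and refill: 92 x 10/410 = 2.2 µg/mL; 48 x 10/410 = 1.2 µg/mL.
- After a second: 2.2 x 10/410 = 0.05 µg/mL; 1.2 x 10/410 = 0.03 µg/mL.

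Each emptying lowers the level 410/10 = 41-fold. On these assumptions the clearest exposure is the first-morning specimen. The documents give no level at which a culture turns negative, so these figures show where the risk lies, not how often a culture is suppressed.

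**Step 2: effect on the rate ratio.** Let s be the share of on-treatment episodes, countable under the definition, whose culture is negative only because of residual drug, with no such masking before treatment. Then

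counted ratio = true ratio x (1 - s).

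The value of s is an assumption. It is not derived from Step 1.

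**Step 3: effect on the test.** Simulation with 15 participants, an assumed mean of 2.5 UTIs per six months, Poisson counts, no true effect, no overdispersion, no regression to the mean and 20,000 trials. Two tests were used: a paired t-test on log(count + 0.5) and an exact conditional test of pooled counts. The nominal rate in the direction of benefit is 2.5%.

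| Assumed s | Counted ratio, true 1.00 | Counted ratio, true 0.70 | False benefit, paired t | False benefit, exact pooled |
|---|---|---|---|---|
| 0 | 1.00 | 0.70 | 2.4% | 1.9% |
| 10% | 0.90 | 0.63 | 5.9% | 5.2% |
| 20% | 0.80 | 0.56 | 12.3% | 12.4% |
| 30% | 0.70 | 0.49 | 23.0% | 24.4% |
| 50% | 0.50 | 0.35 | 60.2% | 67.4% |

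For assumed means of 2 to 3 UTIs, s = 30% gives about 20% to 30%. A true 30% reduction with s = 29% would be counted as 0.70 x 0.71 = 0.50, the design effect. Masking alone would need s = 50% to produce that.

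**The case against.** The strongest reply is that the key link is missing. No suppressing concentration is given, nothing says when symptomatic specimens are taken, and one emptying cuts the level about 40-fold. Being in the treatment period is not the same as having drug in the sample. This stands: it confines the clear risk to first-morning urine and leaves s unknown.

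A reader might infer that the error always favours gentamicin, or that the trial cannot tell prevention from suppression at all. The documents do not support either. Section 6.1.1 describes gentamicin as indicated for a variety of gram-negative infections, so not every culture need be affected. The UTI symptoms listed in Section 8.3.1 include fatigue and cloudy urine, so a culture-negative episode may not be an infection. Clearing bladder bacteria is also the intended effect, so a negative culture may be real prevention. The direction is fixed only for cultures that the drug has suppressed.

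It can also be said that strict use of the culture rule is itself presumed. UTIs are enumerated from the medical record, the entry criterion of two prior UTIs (Section 5.1) mentions no culture, and the SAP does not restate the rule. If pre-treatment UTIs are not held to it, the asymmetry grows. Specimen handling may be covered in the laboratory handbook or the Manual of Operations, which are not available here.

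Finally, the bladder symptom scales are compared pre-post without culture, and UTI symptoms are recorded as adverse events. The scales do not count UTIs, and the adverse event record starts at consent, so neither supplies a matching pre-treatment count.

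**Conclusion.** The point holds as a risk of differential ascertainment, not as a demonstrated bias. The case definition requires a positive culture, treatment-period urine can contain gentamicin, comparison-period urine is free of intravesical prophylaxis, and no planned analysis addresses the difference. Where residual drug suppresses a culture, the counted ratio falls by the factor (1 - s).

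The size is unknown. An assumed s of 10% to 30% gives a counted ratio of 0.90 to 0.70 with no true effect, and a chance of a false conclusion of benefit of about 5% to 24% at 15 participants under the simulation's assumptions. It would be wrong to infer that a reported reduction is an artefact, or that the calculated concentrations justify any value of s. The point merits a supportive analysis and a stated limitation. It does not invalidate the primary endpoint.

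**What to change.** 1. **Supportive sensitivity analysis.** Pre-specify a count of symptomatic UTI episodes with prescribed antibiotic treatment, whatever the culture result. Take it from the medical record only in both periods, because the bi-weekly calls exist only on study and would capture more episodes during treatment than before. Report its rate ratio and confidence interval beside the primary one. It should inform interpretation, not decide whether the primary result stands.
2. **Listing.** List on-treatment symptomatic, treated, culture-negative episodes, with hours since the last instillation where the dosing log (Sections 6.1.2 and 6.4) and a specimen time allow. No section lists specimen times as collected, and Section 1.3 allows for a missing diary, so gaps should be expected.
3. **Stated limits.** The culture-independent count is less specific, and symptom records in the chart may be thin. If prescribing follows the culture result, some masked episodes will be missed here too, so agreement between the two ratios would not fully exclude the bias.

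Specimen collection and UTI care stay with the treating provider, as Section 5.3 sets out; nothing here changes them. The cost is a paragraph in the SAP, a chart review of both periods and one derived variable. The SAP is written in the past tense, so if results are already known, the analysis should be dated and labelled as added afterwards.

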## 4.2 SCIENTIFIC RATIONALE FOR STUDY DESIGN

This study's pre-post design is selected because it provides substantially more statistical power than a parallel group design with a similar sample size and allows participants to serve as their own controls, without requiring them to use placebo for half of the study. Our prior project experience, using a cross-over design indicated that subjects are likely to drop out if they think that they are receiving placebo.

- Treatment (gentamicin plus saline) is administered to each study participant for six months.
- This design provides the benefit of a direct comparison within participants (the effect of no treatment vs. treatment).
- Superiority trial – this design allows one to determine a clinically relevant difference between no intervention and the study intervention.

## 4.3 JUSTIFICATION FOR DOSE

### GENTAMICIN + SALINE

The research pharmacy will send participants premixed bags of 60mg of gentamicin in 50ml of normal saline. Participants will draw 25cc with their syringe, switch tips, instill this into the bladder after emptying of urine at their last evening catheterization, and discard the remaining 25cc of premixed solution. This is equivalent to the 30mg which had been used in the initial study protocol. The solution will remain in the bladder until the next catheterization. This is a standard dose that is easily tolerated by patients, and one that does not lead to leakage. It is based on the clinical expertise of Co-I, [name], and is appropriate for bladders sizes in patients with long-term use of indwelling catheterization.

